8.4.1 Adverse Events

For analysis purposes, AEs will be categorized as pretreatment AEs, treatment-emergent adverse events (TEAEs), or post-treatment AEs:

- **Pretreatment AE:** any AE that started before the first dose of study drug.
- **TEAE:** any AE that increased in severity or that was newly developed at or after the first dose of study drug through the end of TE period.
- **Post-treatment AE:** any AE that increased in severity or that was newly developed after the TE period.

For AEs with a missing or partial start date, if there is no clear evidence that the AEs started (or increased in severity) before or after the first dose date, the start date will be imputed to be the first dose date and the AE will be considered to be a TEAE (see Section 11.7). Similarly, if there is no clear evidence that the AEs started (or increased in severity) before or after the start of the post-treatment period, the start date will be imputed to be the earliest possible time in the TEAE period and the AE will be considered to be a TEAE. As an intermediate step for programming purposes, imputation rules for missing or partially missing AE start/end dates are defined in Section 10.7.

Based on the reported severity and relationship to study drugs, TEAEs can be categorized as follows:

By relationship to the study drugs, treatment emergent adverse events (TEAEs) will be classified into the 4 categories:

- Not related
- Unlikely related
- Possibly related
- Related.

By severity, TEAEs will be classified into the 4 categories:

- **Mild (Grade 1):** Mild level of discomfort and does not interfere with regular activities
- **Moderate (Grade 2):** Moderate level of discomfort and significantly interferes with regular activities
- **Severe (Grade 3):** Significant level of discomfort and prevents regular activities
- **Life-threatening (Grade 4 and 5):** Any adverse drug experience that places the subject, in the view of the investigator, at immediate risk of death.

8.4.1.1 Overview of Pre-treatment AEs and Treatment Emergent AEs

An overview of the pre-treatment AEs will be summarized in the following categories:

- Any pre-treatment AEs
- Grade 3/4 pre-treatment AEs
- Pre-treatment SAEs by severity.

An overview of all TEAEs will be summarized in the following categories:

- Any TEAEs
- Grade 3/4 TEAEs
- TEAEs by relationship
- TEAEs by severity
- TEAEs leading to treatment discontinuation (this category will capture TEAEs leading to discontinuation of either the morning or the evening tablets)
- TEAEs leading to treatment interruption (this category will capture TEAEs leading to interruption of either the morning or the evening tablets)
- TE SAE by severity
- TEAE leading to death

8.4.1.2 TEAEs and TE SAEs by System Organ Class (SOC) and Preferred Term (PT)

The number and percentage of subjects with TEAEs will be summarized by treatment group, MedDRA system organ class (SOC), and preferred term (PT), where multiple occurrences of the same AE for the same subject will be counted only once. The summary table will be presented in descending order of frequencies in the TEZ/IVA treatment group. TE SAEs will be summarized similarly.

8.4.1.3 TEAEs and TE SAEs by Preferred Term (PT)

The number and percentage of subjects with TEAEs will be summarized by treatment group and PT, where multiple occurrences of the same AE for the same subject will be counted

only once. The summary table will be presented in descending order of frequencies in the TEZ/IVA treatment group. TE SAEs will be summarized similarly.

8.4.1.4 TEAEs and TE SAEs by SOC, PT, and Relationship

The number and percentage of subjects with TEAEs will be summarized by treatment group, SOC, PT, and relationship, where multiple occurrences of the same AE for the same subject will be counted only once according to the worst relationship to study drug. The summary table will be presented in descending order of frequencies in the TEZ/IVA treatment group. TE SAE will be summarized similarly.

8.4.1.5 TEAEs and TE SAEs by SOC, PT, and Severity

The number and percentage of subjects with TEAEs will be summarized by treatment group, SOC, PT, and severity, where multiple occurrences of the same AE for the same subject will be counted only once according to the worst severity. The summary table will be presented in descending order of frequencies in the TEZ/IVA treatment group. TE SAE will be summarized similarly.

8.4.1.6 Respiratory Events and Symptoms

Respiratory symptoms are defined as any TEAEs for the following 3 PTs:

- Chest discomfort
- Dyspnoea
- Respiration abnormal

Respiratory events are defined as any of the afore-mentioned respiratory symptoms, or any TEAEs for the following 4 additional PTs:

- Asthma
- Bronchial hyperreactivity
- Bronchospasm
- Wheezing

A summary of respiratory symptoms and events will be presented by preferred term.

8.4.1.7 Elevated Transaminase

The following AE preferred terms will be selected for **elevated transaminase**:

- Alanine aminotransferase abnormal
- Alanine aminotransferase increased
- Aspartate aminotransferase abnormal

- Aspartate aminotransferase increased
- Transaminases abnormal
- Transaminases increased
- Liver function test abnormal
- Liver function test increased
- Hypertransaminasaemia
- Hepatic enzyme abnormal
- Hepatic enzyme increased.

A summary of elevated transaminase will be presented by preferred term.

8.4.1.8 Summaries of Respiratory Events and Elevated Transaminase by Treatment Interval

Respiratory events and elevated transaminase also will be summarized by the following treatment intervals:

- 0-1 Weeks: [Day1, Day7]
- >1 -2 Weeks: [Day8, Day14]
- >2 -8 Weeks: [Day15, Day56]
- >8-16 Weeks: [Day57, Day112]
- >16 -24 Weeks: [Day113, Day168]
- >24 Weeks: [Day169, end of TE period])

8.4.1.9 Subgroup Analysis

TEAEs will be summarized by SOC and PT for the following subgroups:

- Age at screening (<18, ≥18 years)
- Percent predicted FEV₁ at baseline (<40, ≥40-<70, ≥70)
- Sex
- Region (North America, Europe)

Separate listings will be presented for TEAEs leading to treatment discontinuation, TE SAEs, and all deaths.

For all AEs, the CRF captures the action taken for VX661/IVA pills separately from the AE action taken for IVA monotherapy pills. As a result, it is possible that, in the final database (after DBL), the AE actions taken for the two agents (fixed dose TEZ/IVA and ivacaftor monotherapy) are different. The summaries and listings of “AE Leading to Treatment Dis-

continuation” and “AE Leading to Treatment Interruption” account for discontinuation and interruptions for either agent.

8.4.2 Clinical Laboratory Values

For treatment emergent laboratory measurements, the raw values and change from baseline values for the continuous hematology, chemistry and coagulation results will be summarized in SI units by treatment group at each scheduled time point. For hematology, chemistry and coagulation, the number and percentage of subjects with an abnormal low (<LLN) value and with an abnormal high (>ULN) value at each scheduled time point will be summarized.

The number and percentage of subjects with hematology, chemistry and coagulation values meeting the defined threshold criterion will be summarized by treatment, lab parameters, and visit. The threshold criteria are provided in Section 11.5, Table 11-6 and Table 11-7.

For all LFT results (alanine aminotransferase [ALT], aspartate aminotransferase [AST], alkaline phosphatase [ALP], direct bilirubin, total bilirubin, and gamma-glutamyl transferase [GGT]), the following additional analyses will be conducted:

- A listing of subjects with elevated LFT results during the TE period will be presented. For each subject in the listing, LFT assessments at all visits will be included.
- For each of the LFTs, mean values (\pm SD) will be plotted by visit, and a box plot of the LFT value/ULN will be plotted by visit.
- The incidence of LFTs meeting threshold criteria against the baseline threshold criteria also will be summarized by treatment group, LFT parameters, and visit (only shifts to values worse than baseline will be presented).
- A scatter plot of the maximum ALT value across visits versus the maximum total bilirubin value also will be presented. The ALT and total bilirubin values will be presented on a logarithmic scale. The graph will be divided into 4 quadrants with a vertical line corresponding to 3xULN for ALT and a horizontal line corresponding to 2xULN for total bilirubin. A similar graph of maximum AST value versus maximum total bilirubin value will be presented as well.

A summary table for the shift from baseline to the value at Week 24 will be presented by treatment group for vitamin levels and lipid panel. A box plot of vitamin levels and lipid panel also will be plotted against visit.

In addition, a listing containing individual subject hematology, chemistry, and coagulation values outside the reference ranges will be provided. This listing will include data from scheduled and unscheduled time points. Subjects with positive pregnancy test results will be listed. Abnormal urinalysis results also will be listed by treatment and subject.

8.4.3 Standard 12-Lead Electrocardiogram

For treatment-emergent ECG measurements, a summary of raw values and change from period baseline values will be provided by treatment group at each scheduled time point for the following standard 12-lead ECG measurements: PR, QTc for HR intervals (QTcF), QRS

duration, and HR. In addition, the mean value at each time point will be plotted by treatment group for QTcF and heart rate.

The number and percentage of subjects with ECG events meeting threshold criteria during the treatment-emergent period will be summarized by treatment, ECG parameters, and visit. The threshold criteria are provided in Section 11.5, Table 11-8.

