11.7.4 Electrocardiograms

11.7.4.1 Standard 12-Lead Electrocardiograms

Standard 12-lead ECGs will be performed using a machine with printout according to the Schedule of Assessments (Table 3-1 and Table 3-2). Additional standard 12-lead ECGs will be performed at any other time if clinically indicated. The performance of all ECGs will adhere to the following guidelines:

- The subject will be instructed to rest in the supine position for at least 5 minutes before having an ECG performed.
- The ECG will be performed before any other procedures that may affect heart rate, such as blood draws.

The ECG traces will be manually read at the study site at the Screening and Safety Follow-up Visits. A printout of the ECG traces will be made for safety review by the investigator and maintained with source documentation. Clinically significant ECG abnormalities occurring during the study through the Safety Follow-up Visit will be recorded as AEs.

To ensure safety of the subjects, a qualified individual at the study site will make comparisons to baseline measurements. If the QTcF is increased by >45 msec from the baseline or an absolute QTcF value is ≥ 500 msec for any scheduled ECG, 2 additional ECGs will be performed approximately 2 to 4 minutes apart to confirm the original measurement. If either of the QTcF values from these repeated ECGs remains above the threshold value (>45 msec from baseline or ≥ 500 msec), a single ECG will be repeated at least hourly until QTcF values from 2 successive ECGs fall below the threshold value that triggered the repeat measurement.

If the QTcF value remains above the threshold value (>45 msec from the average of the 3 predose values on Day 1 or ≥ 500 msec) on repeated measurement or is noted on >2 occasions with no identified alternative etiology for the increased QTcF study drug, then discontinuation from study drug treatment may be required after discussion with the medical monitor.

Subjects in whom treatment is discontinued for increased QTc should have their QTc monitored closely until it normalizes or returns to baseline.

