12.3.4.2 Clinical Laboratory Assessments

For the treatment-emergent laboratory measurements, the raw values and change from baseline values of the continuous laboratory parameters will be summarized in SI units by treatment group at each scheduled time point. In addition, mean value at each visit will be plotted by treatment groups for each of the liver function parameters.

The number and percentage of subjects with at least 1 potentially clinically significant (PCS) event during the TE period will be summarized by treatment group. The PCS (post-baseline)

shift from baseline will also be summarized for selected laboratory parameters. The PCS criteria and the parameter selection criteria will be provided in the SAP.

Results of urinalysis and the serum pregnancy test will be listed in individual subject data listings only. In addition, a listing containing individual subject laboratory assessment values outside the reference ranges will be provided. This listing will include data from scheduled and unscheduled time points.

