12.3.4.3 Electrocardiogram

For the treatment-emergent ECG measurements, a summary of raw values and change from baseline values will be provided by treatment group at each scheduled time point for the following standard 12-lead ECG measurements: PR, QT, and QTc for HR intervals (QTcF), QRS duration, and HR. In addition, the mean value at each visit will be plotted by treatment groups for QTc.

The number and percentage of subjects with at least 1 PCS event during the TE period will be summarized by treatment group. The PCS criteria will be provided in SAP.

Additional ECG analyses will be described in the SAP.

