8 STATISTICAL ANALYSIS

8.1 General Considerations

All individual subject data in the All Subject Set will be presented in data listings. The Schedule of Assessments is provided in Section 11.1. The precision standards are provided in Section 11.6.

Continuous variables will be summarized using the following descriptive summary statistics: the number of subjects (n), mean, standard deviation (SD), median, minimum value (min), and maximum value (max).

Categorical variables will be summarized using counts and percentages.

Baseline Value, unless otherwise specified, is defined as the most recent non-missing measurement (scheduled or unscheduled) collected prior to or on the first dose of study drug. For ECGs, the baseline will be defined as the average of the 3 pre-treatment measurements (triplicate) on Day 1. For sweat chloride, the baseline value will be the mean of last assessment values on the left and the right arm prior to the first dose of the study drug.

Change (Absolute Change) from baseline will be calculated as Post-baseline value – Baseline value.

Relative change from baseline will be calculated and expressed in percentage as $100 \times (\text{Post-baseline value} - \text{Baseline value}) / \text{Baseline value}$.

Treatment Emergent (TE) Period will include the time from the first dose of study drug to the Safety Follow-up Visit, or to 28 days after the last dose of the study drug for subjects who do not have a Safety Follow-up Visit, or to the last participation date in the study (i.e., the day right before the first study dose in the extension study for subjects who enrolled into the extension study), whichever occurs first. The TE period will be used for safety analyses unless otherwise specified.

Unscheduled Visits: Unscheduled visit measurements will be included in the following:

1. derivations of measurements at scheduled visits per specified visit windowing rules below;
2. derivations of baseline/last on-treatment measurements;
3. derivations of the maximum/minimum on-treatment values and maximum/minimum changes from baseline values for safety analyses;
4. data listings where appropriate.

Visit Windowing Rules: Section 11.2 defines the windows for protocol-defined visits. The windows will be applied using the following rules for both scheduled and unscheduled visits:

1. If no measurement is available within a visit window, the assessment will be considered missing for the visit;

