2. If there is more than one measurement available within the same visit window, use the following rules:
 - For all efficacy parameters, if there are multiple measurements within a visit window, the record at the scheduled visit will be used. Otherwise,
 - The record closest to the target day will be used;
 - If there are multiple records with the same distance to the target day, the latest record will be used.
 - Assessments at early treatment termination (ETT) visit will follow the windowing rules for regular visits up to Week 24.
 - Assessments at safety follow-up (SFU) visit will follow the windowing rules for regular visits if they fall within the upper boundary of the window for

Week 24, or remain as SFU if they go beyond the upper boundary of the window for Week 24.

- For all safety parameters, if there are multiple measurements within a visit window, then 1) the record closest to the target day will be used; 2) if there are multiple records within the same distance from the target day, the latest record will be used; or 3) SFU visit will not be windowed; instead, it will be used according to the nominal visit in relevant analyses.

Note, spirometry assessments, BMI, weight, and height will be used for both efficacy and safety purposes. Their measurements will follow the visit windowing rules for efficacy parameters.

Incomplete/Missing data will not be imputed, unless otherwise specified.

Outliers: No formal statistical analyses will be performed to detect or remedy the presence of statistical outliers, unless otherwise specified.

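### The SAP's threshold tables are by visit with no any-time count, and if they use one windowed record per visit they can miss a QTcF of 500 msec or more that is repeated the same day

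*SAP*

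**What the plan says.** - **Protocol 12.3.4.3 (ECG):** "The number and percentage of subjects with at least 1 PCS event during the TE period will be summarized by treatment group". Protocol 12.3.4.2 opens the laboratory summary in the same way ("The number and percentage of subjects with at least 1 potentially clinically significant (PCS) event during the TE period"), and 12.3.4.4 does so for vital signs.
- **SAP 8.4.3 (ECG):** subjects with "ECG events meeting threshold criteria during the treatment-emergent period will be summarized by treatment, ECG parameters, and visit". SAP 8.4.2 has laboratory "values meeting the defined threshold criterion will be summarized by treatment, lab parameters, and visit", and 8.4.4 follows the same pattern for vital signs. SAP section 3 gives the SAP precedence where methods differ.
- **SAP 8.1 (which record stands for a visit):** unscheduled records enter "derivations of measurements at scheduled visits per specified visit windowing rules below". The rule is "For all safety parameters, if there are multiple measurements within a visit window, then 1) the record closest to the target day will be used"; next, "if there are multiple records within the same distance from the target day, the latest record will be used". For efficacy parameters the scheduled record has priority; for safety parameters it does not.
- **Protocol 11.7.4.1 (QTcF repeats):** a value of 500 msec or more, or more than 45 msec above baseline, leads to two further ECGs 2 to 4 minutes apart. If either is still above the trigger, "a single ECG will be repeated at least hourly until QTcF values from 2 successive ECGs fall below the threshold value".
- **SAP Table 11-8 (QTc rows):** >450 (male), >470 (female) and ≥500 msec; increases of >10, >20, >40 and >60 msec.

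**The concern.** Two things combine.

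First, the protocol's summary, the number of subjects with at least one event, is not carried into the SAP. It cannot be recovered from by-visit rows, because one subject may appear at several visits.

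Second, SAP 8.1 chooses a representative value for each visit. That suits by-visit means but not a count of extremes. The protocol's repeat procedure ends only when QTcF has come down, and the tie rule prefers the last record of the day.

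At stake is the QTcF outlier table, in a programme where Protocol 9.4 notes that no thorough QT study had yet assessed the combination.

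**Working it through.** The plan states no figure on this point, so there is nothing to reproduce. The check applies the SAP 8.1 safety rule to records that follow the protocol's repeat schedules.

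**ECG, Week 8**

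Inputs: target Day 57 and window Days 44 to 71 (SAP 11.2); visit allowed on Days 52 to 62 (±5 days); trigger and stopping rule from Protocol 11.7.4.1. The QTcF values are illustrative.

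Rule: keep the record with the smallest |study day − 57|; on a tie keep the latest. Same-day repeats share a study day and always tie.

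| QTcF sequence on one day (msec) | Record kept | Maximum | ≥500 row, windowed record | ≥500 row, worst value |
|---|---|---|---|---|
| 505, 490, 488 | 488 | 505 | not counted | counted |
| 512, 506, 503, 495, 490 | 490 | 512 | not counted | counted |

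The result is the same on all 11 visit days for both sequences.

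Which Table 11-8 rows are affected follows from where the sequence stops:
- A sequence triggered by ≥500 msec ends below 500, so the ≥500 row loses it. The kept values of 488 and 490 still count in the >450 or >470 row.
- An increase of >60 msec always exceeds the 45 msec trigger, so its sequence ends at 45 msec or less and the >60 row loses it. An ending of +44 msec still counts in the >10, >20 and >40 rows.

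**Scope**

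SAP 11.2 uses nominal visits for Day 1 and Day 15 ECGs, and SAP 8.1 does so for the Safety Follow-up Visit. The tie rule therefore operates at Weeks 4, 8, 12, 16 and 24 only.

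**Laboratory values, Week 8**

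Protocol 11.7.7 places retests at 48 to 72 hours or at 7 ± 2 days, so they are not same-day ties. Let d be the visit's offset from the target day (−5 to +5) and L the lag to the retest. The retest replaces the first value when |d + L| ≤ |d|, that is, when d ≤ −L/2.

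| Lag L (days) | Offsets at which the retest is kept | Count |
|---|---|---|
| 2 | −5 to −1 | 5 of 11 |
| 3 | −5 to −2 | 4 of 11 |
| 5 | −5 to −3 | 3 of 11 |
| 7 | −5, −4 | 2 of 11 |
| 9 | −5 | 1 of 11 |

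Otherwise the first value is kept. Illustration: ALT 4×ULN on Day 57 (distance 0) and 9×ULN on Day 60 (distance 3). Day 57 is kept, Week 8 shows >3 to ≤5×ULN, and the >8 to ≤20×ULN row does not count the subject at that visit.

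**The case against.** The strongest reply is that the loss is inferred and not instructed. SAP 8.4.3 never says that only the windowed record is used, it refers to events during the TE period, and SAP 8.1 lets unscheduled records enter maximum and minimum on-treatment values for safety analyses. A programmer could read this as a worst-value count. That stands as far as it goes: the text is ambiguous. But 8.4.3 does not call on those maxima, and elsewhere the SAP says so when it wants an extreme (maximum ALT in 8.4.2, lowest oxygen saturation in 8.4.5). Two programmers could obtain different QTcF counts.

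It can also be said that Protocol 12.3 leaves presentation details to the SAP. The SAP may therefore depart from the protocol, but nothing in its legible text gives a reason to drop the any-time count.

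Four stronger readings are tempting, and the documents do not support them:
- *Every QTcF exceedance disappears from the table.* Only the ≥500 and >60 msec rows lose it by construction, and only if QTcF resolves that day. Protocol 11.7.4.1 also provides for values that stay high; a last same-day record still above the row's limit is counted.
- *Confirmed events are the most likely to be lost.* The mechanism takes unconfirmed exceedances as well, and a laboratory elevation drawn on the target day is kept.
- *Laboratory tables fail in the same way.* The tie rule is not involved. Peaks also appear in the maximum ALT and AST against bilirubin plots, the elevated-LFT and out-of-range listings (8.4.2) and the transaminase AE summaries (8.4.1.7 and 8.4.1.8).
- *Nothing else would show a high QTcF.* Values appear in the general listings (SAP 8.1), and clinically significant ECG findings are recorded as AEs (Protocol 11.7.4.1). Parts of the SAP are redacted, so the absence of any other output cannot be asserted.

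**Conclusion.** The point holds in limited form. SAP 8.4.2 to 8.4.4 name no any-time threshold count where the protocol specifies one; this does not depend on how SAP 8.1 is read. For QTcF, the ≥500 and >60 msec rows at Weeks 4 to 24 can miss events on three assumptions: the by-visit count uses the windowed record, the repeats are entered as analysable records, and QTcF falls below the trigger the same day. Given these, the loss in the illustrative sequences is complete (11 of 11 visit days). SAP 8.4.3 states no maximum-value QTcF summary that would show the event in aggregate.

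For laboratory values the effect is weaker: a higher retest can be left out, or a retest can replace the first value after an early visit, but other outputs show the peak. How many subjects would be affected in either case cannot be derived from the documents.

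**What to change.** In SAP 8.4.2, 8.4.3 and 8.4.4, add an any-time row for each threshold: the number and percentage of subjects with at least one event in the TE period, by treatment group, as the protocol states. Base it on each subject's worst post-baseline value across all scheduled, unscheduled and repeat records. The maxima and minima already provided for in SAP 8.1 can serve, if the text says that they run over the TE period. Keep the by-visit table as a secondary display, and limit the closest-or-latest rule to by-visit descriptive summaries. Make the change before unblinding.

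The cost is SAP wording and one extra derivation from records already collected. Reported incidences may be slightly higher.
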